# APPENDIX 2. LIST OF CYP3A INHIBITORS

Taken from Table 3, FDA Draft Guidance for Industry: Drug Interaction Studies—Study Design, Data Analysis, Implications for Dosing, and Labeling Recommendations; Feb 2012; updated Sept. 26, 2016). Excluded strong CYP3A4 inhibitors are listed in the far left column of the table.

	Strong Inhibitors	Moderate Inhibitors	Weak Inhibitors
	≥ 5-fold increase in AUC Or, > 80% decrease in CL	≥ 2 but < 5-fold increase in AUC Or 50-80% decrease in CL	≥ 1.25 but < 2-fold increase in AUC Or, 20-50% decrease in CL
CYP3A4	Boceprevir	amprenavir	alprazolam
	clarithromycin	aprepitant	amiodarone
	cobicistat	atazanavir	amlodipine
	conivaptan	cimetidine	atorvastatin
	danoprevir	ciprofloxacin	bicalutamide
	elvitegravir	clotrimazole	chlorzoxazone
	grapefruit juice	crizotinib	cilostazol
	indinavir	cyclosporine	fosaprepitant
	itraconazole	darunavir/ritonavir	fluoxetine
	ketoconazole	diltiazem	gingko
	lopinavir	dronedarone	goldenseal
	mibefradil	erythromycin	isoniazid
	nefazodone	fluconazole	istradefylline
	nelfinavir	fluvoxamine	ivacaftor
	paritaprevir	fosamprenavir	lapatinib
	posaconazole	imatinib	lomitapide
	ritonavir	tofisopam	nilotinib
	saquinavir	verapamil	oral contraceptives
	telaprevir		pazopanib
	telithromycin		ranitidine
	tipranavir		ranolazine
	troleandomycin		tacrolimus
	voriconazole		tipranavir/ritonavir
			ticagrelor
			zileuton
Source: Table	2.2	1	1

Source: Table 3-2,

https://www.fda.gov/Drugs/DevelopmentApprovalProcess/DevelopmentResources/DrugInteractionsLabeling/ucm093664.htm

# APPENDIX 3. AMRIX® PACKAGE INSERT (DATED MAY 2018)

#### HIGHLIGHTS OF PRESCRIBING INFORMATION

These highlights do not include all the information needed to use AMRIX safely and effectively. See full prescribing information for AMRIX.

AMRIX® (cyclobenzaprine hydrochloride extended-release capsules), for oral use initial U.S. Approval: 1977

#### INDICATIONS AND USAGE.

AMRIX is a muscle relaxant indicated as an adjunct to rest and physical therapy for relief of muscle spasm associated with acute, painful musculoskeletal conditions, (1) High of this of Use:
 AMRIX should be used only for short periods (up to 2 or 3 weeks) (1)
 AMRIX has not been found effective in the treatment of spasticity or cerebral palsy (1)

#### -DOSAGE AND ADMINISTRATION

- Recommended adult dose for most patients is 15 mg taken once daily. Some patients may require 30 mg taken once daily (2)
   Recommended to take doses at approximately same time each day (2)
   Instruct patients to swallow AMRIX capsules intact or to sprinkle capsule contents on a tablespoon of applesauce and swallow immediately without chewing (2)
   Use for periods longer than 2 or 3 weeks is not recommended (2)

#### DOSAGE FORMS AND STRENGTHS Extended-release capsules: 15 and 30 mg (3)

- -CONTRAINDICATIONS
- Hypersensitivity to any component of this product (4)
   Concomitant use of monoamine oxidase (MAO) inhibitors or within 14 days after their discontinuation (4)
- During acute recovery phase of myocardial infarction, and in patients with arrhyth-mias, heart block or conduction disturbances, or congestive heart failure (4)
- Hyperthyroidism (4)

#### AMRIX® (cyclobenzaprine hydrochloride extended-release capsules)

- Serotonin syndrome has been reported with cyclobenzaprine when used in combination with other serotonergic drugs (5.1)
  Cyclobenzaprine is structurally related to tricyclic antidepressants which have been
- reported to produce adverse cardiovascular effects or CNS depressant effects (5.2) Use in the elderly is not recommended (5.3)

- Use in patients with hepatic impairment is not recommended (5.4)
   Use with caution in patients with a history of urinary retention, angle-closure glaucoma, increased intraocular pressure and in patients taking anticholinergic

#### -ADVERSE REACTIONS

Most common adverse reactions (incidence ≥3% in any treatment group and greater than placebo): dry mouth, dizziness, fatigue, constipation, nausea, dyspepsia, and

To report SUSPECTED ADVERSE REACTIONS, contact Teva Pharmaceuticals at [name] or FDA at [name] or www.fda.gov/medwatch.

#### -DRUG INTERACTIONS

- MAO Inhibitors: Life-threatening interactions may occur (4, 7)
   Serotonergic Drugs: Serotonin syndrome has been reported (5.1, 7)
   CNS Depressants: Effects of alcohol, barbiturates, and other CNS depressants may be enhanced (5.2, 7)
- Tramadol: Seizure risk may be enhanced (7) Guanethidine: Antihypertensive effect may be blocked (7)

See 17 for PATIENT COUNSELING INFORMATION and FDA-approved patient labeling.

Revised: 5/2018

### **FULL PRESCRIBING INFORMATION**

#### INDICATIONS AND USAGE

AMRIX® (cyclobenzaprine hydrochloride extended-release capsules) is indicated as an adjunct to rest and physical therapy for relief of muscle spasm associated with acute, painful musculoskeletal conditions. Improvement is manifested by relief of muscle spasm and its associated signs and symptoms, namely, pain, tenderness, and limitation of motion.

- Limitations of Use:
   AMRIX should be used only for short periods (up to two or three weeks) because adequate evidence of effectiveness for more prolonged use is not available and because muscle spasm associated with acute, painful musculoskeletal conditions is generally of short duration and specific therapy for longer periods is seldom
- AMRIX has not been found effective in the treatment of spasticity associated with cerebral or spinal cord disease or in children with cerebral palsy.

### DOSAGE AND ADMINISTRATION

The recommended adult dose for most patients is one (1) AMRIX 15 mg capsule taken once daily. Some patients may require up to 30 mg/day, given as one (1) AMRIX 30 mg capsule taken once daily or as two (2) AMRIX 15 mg capsules taken

It is recommended that doses be taken at approximately the same time each day. Use of AMRIX for periods longer than two or three weeks is not recommended [see Indications and Usage (1)].

Instruct patients to swallow AMRIX capsules intact. Alternatively, the contents of the

AMRIX capsule may be sprinkled over applesauce and then swallowed. This method is appropriate only for patients able to reliably swallow the applesauce without chewing.

Other foods have not been tested and should not be substituted for applesauce. Notes that the patient to:
 Sprinkle the contents of the capsule onto a tablespoon of applesauce and consume

- immediately without chewing.
  Rinse the mouth to ensure all of the contents have been swallowed.
- Discard any unused portion of the AMRIX capsules after the contents have been sprinkled on applesauce.

3 DOSAGE FORMS AND STRENGTHS
Extended-release capsules in the following strengths:

- 15 mg: Capsules are orange/orange and are embossed in blue ink with "15 mg" on the body, and Cephalon "C" logo, "Cephalon," and a dashed band on the cap.
   30 mg: Capsules are blue/red and are embossed in white ink with "30 mg" on the body, and Cephalon "C" logo, "Cephalon," and a dashed band on the cap.

### CONTRAINDICATIONS

- . Hypersensitivity to any component of this product. These adverse reactions may
- manifest as an anaphylactic reaction, urticaria, facial and/or fongue swelling, or pruritus. Discontinue AMRIX if a hypersensitivity reaction is suspected. Concomitant use of monoamine oxidase (MAO) inhibitors or within 14 days after their discontinuation. Hyperpyretic crisis seizures and deaths have occurred in patients receiving cyclobenzaprine (or structurally similar tricyclic antidepressants) concomitantly with MAO inhibitor drugs.

  • During the acute recovery phase of myocardial infarction, and in patients with
- arrhythmias, heart block or conduction disturbances, or congestive heart failure.
- Hyperthyroidism

#### WARNINGS AND PRECAUTIONS

5.1 Serotonin Syndrome
The development of a potentially life-threatening serotonin syndrome has been reported with cyclobenzaprine when used in combination with other drugs, such as selective serotonin reuptake inhibitors (SSRIs), serotonin norepinephrine reuptake inhibitors (SNRIs), tricyclic antidepressants (TCAs), tramadol, bupropion, meperidine, verapamil, or MAC inhibitors. The concomitant use of AMRIX with MAO inhibitors is ontraindicated [see Contraindications (4)]. Serotonin syndrome symptoms may include mental status changes (e.g., confusion, agitation, hallucinations), autonomic instability (e.g., diaphoresis, tachycardia, labile blood pressure, hyperthermia), neuromuscular abnormalities (e.g., tremor, ataxia, hyperreflexia, clonus, muscle rigidity), and/or gastrointestinal symptoms (e.g., nausea, vomitting, diarrhea). Treatment with AMRIX and any concomitant serotonergic agents should be discontinued in the discontinued of the continued of th immediately if the above reactions occur and supportive symptomatic treatment should be initiated. If concomitant treatment with AMRIX and other serotonergic drugs is clinically warranted, careful observation is advised, particularly during treatment initiation or dose increases.

#### Tricyclic Antidepressant-like Effects

Cyclobenzaprine is structurally related to the tricyclic antidepressants, e.g., amitripty-line and imipramine. Tricyclic antidepressants have been reported to produce arrhythline and impramine. Incyclic antidepressants have been reported to produce armyn-mias, sinus tachycardia, prolongation of the conduction time leading to myocardial infarction and stroke [see Contraindications (4)]. AMRIX may enhance the effects of alcohol, barbiturates, and other CNS depressants. Some of the more serious central nervous system (CNS) reactions noted with the tricyclic antidepressants have occurred in short-term studies of cyclobenzaprine for indications other than muscle spasm associated with acute musculoskeletal condi-

tions, and usually at doses somewhat greater than those recommended for skeletal muscle spasm. If clinically significant CNS symptoms develop, consider discontinuation of AMRIX.

uation of AMHIX.

5.3 Use in the Elderly
As a result of a 40% increase in cyclobenzaprine plasma levels and a 56% increase in plasma half-life following administration of AMRIX in elderly subjects as compared to young adults, use of AMRIX is not recommended in the elderly [see Clinical Pharmacology (12.3)].

5.4 Use in Patients with Hepatic Impairment

5.4 Use in Patients with repatic impairment.
As a result of two-fold higher cyclobenzaprine plasma levels in subjects with mild hepatic impairment, as compared to healthy subjects, following administration of immediate-release cyclobenzaprine and because there is limited dosing flexibility with AMRIX, use of AMRIX is not recommended in patients with mild, moderate, or severe hepatic impairment [see Clinical Pharmacology (12.3)]

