## 7.2. Inclusion Criteria

- 1. The patient has either a) completed the double-blind lead-in study and completed or is active (at the time of study discontinuation) in the 12-week open-label extension study (P303), or b) is currently enrolled in the double-blind lead-in study that was discontinued due to results of an interim analysis, and is judged by the investigator as reasonably compliant, with at least 60% compliance with study medication usage (based on drug accountability).
- 2. The patient has provided written informed consent to participate in this extension study. *Note:* Separate written, signed informed consent will be required if the patient is to participate in the optional pharmacogenomic assessment. A decision not to participate in the optional pharmacogenomic testing will not affect the patient's eligibility for the main study.
- 3. The patient met all prior inclusion and exclusion requirements for the double-blind leadin study, or the site received medical monitor approval for the patient to remain in the lead-in study after the retrospective discovery of an entry violation that did not pose any threat to the patient's safety or well-being.
- 4. During the course of the lead-in study or 12-week open-label extension study, the patient has had no intervening medical conditions including pregnancy, clinically significant increase in suicidal ideation (plan or intent) or significant worsening of depression, newly arising clinically significant abnormal laboratory tests, or any clinically significant, uncontrolled, or unstable medical or surgical condition that could affect the patient's ability to participate in the study or potentially compromise the patient's well-being during the study.
- 5. The patient does not require treatment with a potent (strong) cytochrome P450 subtype 3A4 (CYP3A4) inhibitor, or St. John's wort.
- 6. The patient is willing to refrain from use of all other formulations of cyclobenzaprine for the duration of the study.
- 7. The patient is willing to refrain from use of monoamine oxidase inhibitors for the duration of the study.
- 8. Female patients of childbearing potential continue to agree to practice one of the medically acceptable methods of birth control detailed in the lead-in study.

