## For all patients:

- Obtain written informed consent to participate
- Inclusion criteria
- Review and transcribe new concomitant medications as well as those which are to be continued from the double-blind lead-in HONOR study or the 12-week open-label extension study P303
- Review and transcribe new AEs as well as those which are ongoing from the doubleblind lead-in HONOR study or the 12-week open-label extension study P303

For patients enrolling from the double-blind lead-in study, P301/HONOR only (or patients rolling over to study P306 more than 14 days after the final visit of the 12-week open-label extension study P303):

- Obtain vital signs, including weight. The height collected at baseline from the lead-in study will be utilized for body mass index (BMI) calculations in this study.
- Perform a visual exam of the oral cavity
- Have the patient complete the PROMIS-Sleep Disturbance scale and the SDS.
   Review each scale for completeness once done.
- Have the patient complete the BDI-II
- Conduct the C-SSRS after reviewing the results of the BDI-II
- Draw blood for clinical laboratory testing
- Review patient's lifetime psychiatric treatment history, demographic information and medical history to ensure the information recorded during the double-blind lead-in study is accurate and complete, as it will also be included in the extension study's database.

Only those patients meeting all of the inclusion criteria will be eligible to continue.

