## For all patients:

After all study requirements for Visit 1 of P306 have been fulfilled, the patient will:

- Be dispensed 3 bottles of TNX-102 SL tablets and be instructed to begin dosing with study medication at bedtime, starting the evening of Visit 1;
- Receive instruction regarding proper sublingual dosing technique and the time of expected dosing; and
- Schedule the telephone Visit 2 (for patients enrolled from the double-blind lead-in study, P301/HONOR, only) and receive an appointment to return to the clinic for Visit 3.

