## 10. STUDY ASSESSMENTS

## **10.1.** Screening Assessments

The results of the screening assessments should be reviewed to ensure that the patient continues to satisfy all entry criteria and otherwise remains a satisfactory patient for the extension study. Laboratory assessments obtained at the final visit of the double-blind lead-in HONOR study or the 12-week open-label extension study P303 will not be available prior to the patient's entry into the extension study, but should be reviewed within 7 days when they become available, to ensure the patient's ongoing well-being.

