12.3 Long-Term Vital Signs Analyses

Descriptive summaries of actual values and change from baseline to the minimum post-baseline value, maximum post-baseline value, and final value in the long-term analysis period will be summarized for weight, BMI, body temperature, pulse rate, systolic blood pressure and diastolic blood pressure.

Clinically notable vital signs in the long-term analysis period will be identified based on the criteria below. The number and percentage of subjects with at least 1 treatment-emergent value (i.e., not present at baseline) meeting the criteria below will be tabulated, using the worst post-baseline value in either direction.

Clinically Notable Vital Sign Categories

Vital Sign Parameter	Value
Heart rate	≥130 bpm
	<55 bpm
Systolic Blood Pressure	≥160 mg Hg
	≤90 mm Hg

Protocol: TNX-CY-P306 Page 27 of 36

Final v1.0

Diastolic blood pressure	≥100 mg Hg
	≤60 mm Hg

bpm = beats per minute

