12.4 Long-Term Clinical Laboratory Evaluations

Descriptive summaries of actual values and change from baseline to the minimum post-baseline value, maximum post-baseline value, and final value in the long-term analysis period will be summarized for chemistry and hematology parameters.

A summary of treatment emergent shifts will compare the baseline L/N/H classification for each laboratory test to the highest and/or lowest L/N/H classification post-baseline in the long-term analysis period.

Additionally, subject counts of any post-baseline elevated alanine aminotransferase (ALT), aspartate aminotransferase (AST), bilirubin, and alkaline phosphatase (ALP) will be presented in a separate table, as follows.

Table 7-1 Elevated Liver Function Test Categories

Clinical Laboratory Parameter	Category
ALT	≥3 × ULN; ≥5 × ULN
AST	≥3 × ULN; ≥5 × ULN
ALT or AST	≥3 × ULN; ≥5 × ULN
ALP	≥1.5 × ULN
Total bilirubin	≥ULN; ≥2 × ULN
Total bilirubin elevation with ALT or AST elevation at any post-baseline timepoint(s)	(ALT or AST ≥3 × ULN) and (total bilirubin ≥2 × ULN)
Concurrent total bilirubin elevation with ALT or AST elevation and ALP <2 × ULN [1] ("potential Hy's law cases")	(ALT or AST \geq 3 × ULN) and ALP $<$ 2 × ULN and (total bilirubin \geq 2 × ULN)

ALP = alkaline phosphatase; ALT = alanine aminotransferase; AST = aspartate aminotransferase; ULN = upper limit of normal

Potential Hy's law cases (based on the recommendation in "Guidance for Industry Drug-Induced Liver Injury: Premarketing Clinical Evaluation") will be identified as subjects with post-baseline ALT or AST \geq 3 x upper limit of normal (ULN) and total bilirubin \geq 2 x ULN and ALP <2 × ULN on the same date, as noted above. Liver function test data on any subjects with ALT or AST \geq 3 × ULN will be listed, and any potential Hy's law cases will be specifically identified.

To assess cases potentially meeting requirements for Hy's Law, an evaluation of druginduced serious hepatotoxicity plot of bilirubin against peak ALT will be generated by treatment group, as described by Watkins et al (2008). This plot will be reproduced for

^[1] Concurrent means on the same date.

Protocol: TNX-CY-P306 Page 28 of 36

Final v1.0

peak AST vs. peak total bilirubin, as well as for the greater of peak AST and peak ALT vs. peak total bilirubin.

Protocol: TNX-CY-P306 Page 29 of 36

Final v1.0

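### SAP 12.4 counts liver-test elevations on TNX-102 SL without regard to the pre-drug value, although SAP 12.3 applies a baseline condition to vital signs

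*Protocol*

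**What the plan says.** **SAP Section 12.** The opening of Section 12 sets one baseline for 12.3 and 12.4: the latest value before a patient's first ever TNX-102 SL dose, in whichever of the three studies that fell. Apart from disposition, results are shown for the TNX-102 SL group alone. Patients given placebo in P301 lose their P301 data, except for a baseline record.

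**SAP 12.3 (vital signs).** A patient is counted for having "at least 1 treatment-emergent value (i.e., not present at baseline) meeting the criteria below".

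**SAP 12.4 (liver tests).** The rule is that "subject counts of any post-baseline elevated alanine aminotransferase (ALT), aspartate aminotransferase (AST), bilirubin, and alkaline phosphatase (ALP) will be presented in a separate table". The rows are ALT, AST, and either of the two at 3x and 5x ULN; ALP at 1.5x; bilirubin at 1x and 2x; and two combined rows, the second being potential Hy's law cases. The section also plans change from baseline to the minimum, maximum and final value, a shift summary by low/normal/high class, peak-value plots, and a listing for patients with ALT or AST at 3x ULN or more.

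**Protocol, on entry.** Criterion 4 in 7.2 rules out "newly arising clinically significant abnormal laboratory tests" during the lead-in study or P303. Section 9.1.5 adds: "Only those patients meeting all of the inclusion criteria will be eligible to continue". Section 10.1 says that final-visit results from HONOR or P303 "will not be available prior to the patient's entry into the extension study, but should be reviewed within 7 days when they become available". Under 9.1.5 the patient is to "be instructed to begin dosing with study medication at bedtime, starting the evening of Visit 1".

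**Protocol Appendix 3 (AMRIX label, section 5.4), as background.** The label of this other cyclobenzaprine product says that "use of AMRIX is not recommended in patients with mild, moderate, or severe hepatic impairment".

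**The concern.** The liver table will be read as a count of liver signals on TNX-102 SL over the long-term period. Section 12 has no comparison group, so the patient's own pre-drug value is the only thing against which a case can be discounted. The plan defines that value and uses it for vital signs, but not in this table. A patient who was already above a category before any TNX-102 SL, and is above it again later, looks the same as a patient who crossed it on drug.

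At the higher multiples of ULN the expected counts are low, so one or two pre-existing cases could change how a row is read.

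The entry question is separate. The laboratory part of criterion 4 has to be judged before the most recent result exists, and the protocol does not say which sample decides it.

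**Working it through.** **1. A figure to reproduce.** There is none. Protocol 12.3 and SAP 5 say that no sample size was calculated, and neither document gives an expected rate of liver elevations. The check is therefore mainly of the text.

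**2. The two counting rules under one baseline.**

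| | SAP 12.3 | SAP 12.4 liver table |
|---|---|---|
| Baseline | Last value before first TNX-102 SL | Same |
| Group shown | TNX-102 SL only | Same |
| Counted | Value meets the criterion and did not at baseline | Any later value meets the criterion |

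The baseline value itself is never counted under 12.4. The elevation has to persist or recur after the first dose.

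**3. Do the other outputs in 12.4 separate old from new?**

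| Row | Low/normal/high shift | Liver listing |
|---|---|---|
| ALT, AST, or either, 3x and 5x ULN | No | Yes |
| ALP 1.5x ULN | No | Only if ALT or AST also reaches 3x |
| Bilirubin at ULN | Largely yes | Only if ALT or AST also reaches 3x |
| Bilirubin 2x ULN | No | Only if ALT or AST also reaches 3x |
| Combined and Hy's law rows | No | Yes |

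Take ALP as the example. One patient is above 1.5x ULN both before drug and later. Another is just above ULN before drug and above 1.5x later. Both are high-to-high in the shift summary and both are counted in the 1.5x row, but only the second is new at that level. Summary statistics of change, and plots of peak values, do not sort patients by baseline category either.

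**4. Does SAP 10.2 fill the gap?** Not for patients who had TNX-102 SL before P306. Section 10 is confined to P306 data, and SAP 7.1 sets its baseline as the last value before the first P306 dose. For those patients that value already follows exposure, so the 10.2 shift tables answer a different question.

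**5. Size, for illustration only.** Let N be the patients in the table, q the share at or above a category before drug, and r the share of those who are at or above it again later. Then:

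- expected pre-existing cases counted = N x q x r
- chance of at least one = 1 - (1 - q x r)^N

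The cap N = 200 is from Protocol 6.2. The values q = 0.5% to 2% and r = 25% to 100% are assumptions, as are the smaller N.

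| N | Low: q x r = 0.005 x 0.25 = 0.00125 | High: q x r = 0.02 x 1 = 0.02 |
|---|---|---|
| 50 | 0.06 cases; 6% | 1.0 case; 64% |
| 100 | 0.13 cases; 12% | 2.0 cases; 87% |
| 200 | 0.25 cases; 22% | 4.0 cases; 98% |

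Under a rule like that of 12.3, the number of such cases in the treatment-emergent count would be 0.

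**6. Where the entry sample sits.** Under the Section 12 baseline, the P306 entry sample is pre-drug only for HONOR placebo patients who come directly into P306. Their Visit 1 step is "Draw blood for clinical laboratory testing". For patients on TNX-102 SL in HONOR, or dosed in P303, the entry sample comes after exposure.

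**The case against.** The best defence of 12.4 is that it is an openly inclusive safety display. Counting every post-baseline elevation misses nothing, and differing from the vital-sign rule is a choice rather than a contradiction. The listing also lets a reader trace the liver data of each patient with ALT or AST at 3x ULN or more, which takes in the Hy's law cases. That is fair, and is why the point is an improvement and not an error that undermines the analysis. It does not make the counts in the table interpretable, and isolated ALP or bilirubin elevations fall outside the listing.

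A reader might infer three stronger things that the documents do not support.

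- *That criterion 4 cannot keep out a patient with abnormal liver tests, against the label's warning.* Criterion 4 spans the whole lead-in or P303 period, so results already known can exclude a patient. Criterion 3 carries HONOR's entry criteria forward, subject to medical monitor approval of an entry violation; whether these included a hepatic criterion cannot be seen here. Only the latest sample is late. The statement that "use of AMRIX is not recommended in patients with mild, moderate, or severe hepatic impairment" concerns another product, rests partly on that product's limited dosing flexibility, and is about hepatic impairment, which is not the same as an abnormal liver test.
- *That an abnormal late result goes unattended until the next scheduled test at Week 28 (Day 196 +/- 7).* Protocol 10.1 requires review within 7 days, 10.4.1.5 requires follow-up of clinically significant values, 9.7 allows unscheduled visits, and 9.6 allows removal of a patient. What is missing is the eligibility classification of such a patient.
- *That an elevation in the entry sample is then wrongly counted as on drug.* This link exists only for HONOR placebo patients entering directly. For the others, an elevation at entry is properly on drug unless it was already present at their earlier baseline.

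**Conclusion.** The point holds for the SAP 12.4 liver table. It counts elevations without a baseline condition in an uncontrolled summary, and the other planned outputs do not fully separate new from pre-existing cases at ALP 1.5x, bilirubin 2x, or ALT/AST 3x and 5x ULN. This applies to every patient in Section 12 with a pre-drug value, whatever the route of entry.

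The number of patients affected cannot be derived from the documents. The range of 0.25 to 4.0 cases among 200 rests wholly on assumed prevalence and persistence, and its width shows how little the documents settle; at the higher thresholds the true number is probably small. The bilirubin row at ULN is no measure of the problem, because the shift summary already largely shows baseline status there.

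The entry question is a minor clarification. Criterion 4 and Section 9.1.5 presuppose a laboratory judgement that Section 10.1 says cannot yet use the final-visit result.

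**What to change.** **SAP 12.4.** Present each liver category by status at the pre-drug baseline. Patients below the category at baseline give the treatment-emergent count, and patients at or above it go in a separate row. State how a patient with no pre-drug value is shown. Keep the total for any post-baseline elevation, the Hy's law identification, the plots and the listing, so that nothing is lost. The cost is one extra row block and smaller headline counts.

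**Protocol, minor.** Reconcile 7.2 criterion 4 and 9.1.5 with 10.1 by stating which laboratory sample decides the laboratory part of the criterion. The cost is one clarifying sentence. How a patient with a late abnormal result is managed is for the sponsor and investigator, and no clinical rule is proposed here.
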